We expect that at least 400 patients (of the planned 775 to be accrued) will have a) viable tissue from the surgical specimen, b) paired blood specimens from baseline and after treatment completion, and c) have successful assay. Assuming the 400 patients with surgical specimen and blood specimens are representative of the whole study population, it is expected that about 100 RFS events will occur to the 400 patients. The prospective and large-scale nature of this proposal, in a selected high-risk patient population with complete clinical annotation, is a unique opportunity to successfully identify factors that predict chemotherapy resistance and recurrence. This would be further enriched thanks to the ability to analyze paired tissue and plasma-based molecular results, which would be invaluable to gain insights into tumor evolution and mechanisms of resistance to chemotherapy. Early and accurate detection of patients at highest risk sets the stage for additional therapeutic interventions in the adjuvant setting. The nature of these interventions can be guided by the comprehensive genomic analysis proposed, where certain molecular alterations could be readily actionable, while others may give insight into development of novel therapeutics. Ultimately, these novel approaches will significantly impact risk of recurrence and mortality in this group of patients at highest risk, which is our overall goal.

1.7.1 **Genomic Alterations in the Surgical Tumor.** We aim to determine if genomic alterations identified via profiling of the surgical tumor specimen of patients in the EA1131 clinical trial correlates with RFS. DNA and RNA will be extracted from the surgical specimens and subjected to whole exome sequencing (WES) and if feasible, RNA-sequencing (RNA-seq) analysis. Genomic alterations identified via profiling (i.e., mutations, CNV) will be correlated with RFS. Full

sequencing of residual TNBC in large scale will likely mirror the genomic make-up of metastatic recurrences. We expect that the large-scale identification of tissue genomic biomarkers of chemotherapy sensitivity and resistance will increase our ability to predict which patients with TNBC are at highest risk of relapse after surgery and identify clinically actionable alterations.

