- The futility monitoring rule based on Jennison and Turnbull repeated confidence interval (RCI) method is changed to be more conservative: The rule now is that if the lower boundary of the two-sided 95% RCI for the observed hazard ratio is greater than 0.754 (i.e., the alternative hypothesis) for arm B/arm C and the conditional power of rejecting $HR \geq 1.154$ (H_0) when $HR = 0.754$ (H_a) is less than 10%, then the trial would be stopped due to futility.
- Correlative biomarker blood studies about CTC (secondary correlative objective) added to the protocol.

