9.5 Biomarker Correlative Study

For this correlative biomarker study, we will combine all the patients on all the arms since we don't expect the prognostic value of the biomarkers of interest (i.e., tumor genomic alterations, CTCs) will differ by type of chemotherapy patients received and the intrinsic subtype. The total sample size is 775 patients for EA1131 (562 basal-like patients, 158 non-basal-like patients and 35 patients with unknown subtype). As of June 2019, about 260 patients have enrolled to the study. Taking into consideration of various factors (continuous enrollment in the upcoming months, assay failure, etc.), we expect to have successful genomic profiling of the surgical specimens from at least 400 patients at the end of the study. Per the study protocol, the final analysis of the primary endpoint of the EA1131 trial will take place at 3 years after accrual completion. At the final analyses time (6.9 years after study activation), 196 IDFS events (including recurrence, contralateral breast cancer, second invasive primary cancer, and death) are expected to have occurred to the 562 basal-like TNBC patients based on the alternative hypothesis of the EA1131 study. Of the 196 IDFS events, it is expected that approximately 75% will be recurrence or death, i.e., relapse-free survival (RFS) events. Assuming the same distribution of RFS in the 158 non-basal-like patients and in the 35 patients with unknown subtype, there will be approximately 100 RFS events occurred to the 400 patients with successful genomic profiling, assuming success of genomic profiling is independent of risk of recurrence and basal-like subtype.

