We will determine the proportion of, and factors associated with CTC detection at baseline in early stage TNBC. We will also assess the proportions of patients whose CTCs disappear or persist after chemotherapy. We will evaluate the association between detection of CTC after completion of chemotherapy and RFS and see whether persistence of CTC after chemotherapy can predict disease recurrence. We will also evaluate the association between change in CTC and RFS to see whether lack of decrease in CTC can predict higher risk of recurrence.

In order to test the hypothesis about CTC and RFS, research blood is mandatory for all patients enrolled in the trial, and all patients with research blood and successful assay results about CTC will be included in the analysis. Of the 400 patients with successful CTC detection at baseline and after completion of chemotherapy, we expect that about 35% of them will have detectable CTCs after completion of adjuvant chemotherapy. CTC detection will be coded as a binary variable (positive versus negative), and presence of CTC is defined as any detectable CTC, e.g., ≥ 1 CTC in 7.5 ml blood. With 100 RFS events at the analysis time (assuming no RFS event before

completion of chemotherapy), the minimal HR for presence of CTC versus absence of CTC that could be detected with 80% power at two-sided type I error of 0.05 will be 1.75. The minimal HR that can be detected with 80% power will be 1.85, 1.80, 1.77, and 1.76 if the proportion of CTC is 20%, 25%, 30% and 45%, respectively.

Associations between detection of CTC at completion of chemotherapy as well as change over the course of therapy and RFS will be analyzed using Cox proportional hazard models. Available potential confounding variables will be adjusted in the Cox models. Landmark method will be used for these analyses with landmark time point at 5 months (i.e., completion of chemotherapy in both arms). Factors associated with CTC detection at baseline will be analyzed using Chi square test and Logistic regression models. Due to the exploratory nature of the study, no adjustment will be made for multiple comparisons. All testes will be two-sided with significance level of 0.05.

Rev. Add7

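### The CTC power statement in Section 9.5.2 carries over 100 RFS events from a whole-trial rate. On the plan's own inputs, about 85 countable events are expected, so the detectable HR is about 1.82, not 1.75.

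*Combined protocol and SAP*

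**What the plan says.** Section 9.5 derives about 100 RFS events. It takes 196 IDFS events in 562 basal-like patients, counts 75% of them as RFS events, and applies that rate to 400 patients with successful genomic profiling.

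Section 9.5.2 uses the same two numbers for CTCs. It starts "Of the 400 patients with successful CTC detection at baseline and after completion of chemotherapy", adds "we expect that about 35% of them will have detectable CTCs after completion of adjuvant chemotherapy", and continues "With 100 RFS events at the analysis time". A parenthesis there assumes that no RFS event precedes the end of chemotherapy. The minimum HR that "could be detected with 80% power at two-sided type I error of 0.05 will be 1.75"; values of 1.85, 1.80, 1.77 and 1.76 follow for 20%, 25%, 30% and 45% positivity. The analysis is a landmark analysis, with "landmark time point at 5 months".

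On who can supply CTC data, the opening of Section 9 lists among the Amendment 7 changes: "Correlative biomarker blood studies about CTC (secondary correlative objective) added to the protocol". Section 9.5 reports: "As of June 2019, about 260 patients have enrolled to the study". Section 1.7.2 requires CTC counts to be made in real time. Section 1.7 makes the linking assumption openly: "Assuming the 400 patients with surgical specimen and blood specimens are representative of the whole study population".

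**The concern.** Tissue is mandatory for every patient, so a whole-trial event rate is reasonable for the genomic cohort. It does not carry over to CTCs. Blood for real-time CTC counting cannot be obtained in arrears, so CTC patients come from about the last 775 - 260 = 515 enrolled. At any common analysis date they have been followed for less time than the trial average, and the representativeness assumption in Section 1.7 does not fit them.

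The landmark adds to this. A patient must be free of recurrence at 5 months to enter the analysis, so only later events count. The plan's hazards imply some early events, whereas Section 9.5.2 assumes none.

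The association of CTCs with RFS is a listed secondary correlative objective (Sections 2.3.4 and 2.3.5), and it requires research blood from every patient. A null result should be judged against the effect that this cohort can actually detect.

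**Working it through.** **Inputs from the plan.** 4-year IDFS of 67% on capecitabine and HR 0.754 under the alternative (Section 9.2.1.1); 3.9 years of accrual plus 3 years of follow-up; RFS events as 75% of IDFS events (Section 9.5); 400 evaluable patients, 35% positive, two-sided 0.05 (Section 9.5.2). Added assumptions: exponential times, uniform accrual, and the same 75% share before and after the landmark.

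**1. The plan's event count.** 400 x 0.75 x 196/562 = 104.6, which the plan rounds to about 100.

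**2. The model matches the plan.** Hazards are -ln(0.67)/4 = 0.1001 and 0.754 x 0.1001 = 0.0755 per year. Averaging 1 - exp(-hazard x follow-up) over uniform entry from 0 to 3.9 years, with analysis at 6.9 years, gives 0.348 across the arms. 562 x 0.348 = 195.6 events, against the planned 196.

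**3. The plan's power.** Freedman's formula with unequal groups, k = p/(1 - p), is

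power = Φ( sqrt(d·k)·(HR - 1)/(1 + k·HR) - 1.96 ).

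For p = 0.35, k = 0.538. With d = 100 and HR 1.75: 7.338 x 0.75/1.942 - 1.96 = 0.874, so power is 80.9% and the minimum HR is 1.74. The stated 1.75 is reproduced.

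**4. Late start only.** On uniform accrual, patient 260 enters at 3.9 x 260/775 = 1.31 years. Averaging over entry from 1.31 to 3.9 years gives an IDFS proportion of 0.312, and 400 x 0.75 x 0.312 = 93.5 RFS events. Power at HR 1.75 is 78.2%; the minimum HR is 1.77.

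**5. Late start and landmark.** For patients event-free at 5 months, the proportion with a later event is 0.286, so 400 x 0.75 x 0.286 = 85.9 events. At 6 months, when the second sample is drawn, it is 0.281 and 84.3 events. Power at HR 1.75 is 74.7% and 73.9%; the minimum HR is about 1.82 in both cases. The same hazards imply about 11 RFS events per 400 patients by 5 months and 13 by 6 months, where Section 9.5.2 assumes none.

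**6. Other prevalences** (minimum HR at 80% power):

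| CTC-positive | Stated, 100 events | Freedman, 100 events | Freedman, 85 events |
|---|---|---|---|
| 20% | 1.85 | 1.81 | 1.90 |
| 25% | 1.80 | 1.77 | 1.85 |
| 30% | 1.77 | 1.75 | 1.83 |
| 35% | 1.75 | 1.74 | 1.82 |
| 45% | 1.76 | 1.75 | 1.84 |

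The formula runs up to 0.04 below the stated values at low prevalence. The like-for-like rise is 0.08 to 0.09 throughout.

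**7. Choice of formula.** From 100 to 85.8 events, power falls from 80.9% to 74.7% (Freedman), from 79.9% to 73.6% (log-rank variance at the alternative) and from 76.1% to 69.6% (Schoenfeld, which does not reproduce the stated HR). The loss is about 6 points each way.

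**The case against.** Much can be said for the plan.

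- **The late start alone costs little.** It takes power from 80.9% to 78.2%, partly because 104.6 had already been rounded down to 100. A reader might infer that the Amendment 7 timing by itself defeats the 80% claim. It does not; more than half of the loss comes from the landmark.
- **The landmark simplification is disclosed.** That is true, but disclosure does not make the figure right. The landmark is the planned analysis, and the plan's own hazards contradict the assumption of no early events.
- **400 is not a cap.** All patients with blood and a successful assay are included. However, about 428 of 515 evaluable patients would be needed for 100 events without the landmark, and about 466 (90%) for 100 post-landmark events. The plan expects 400, or 78%.
- **The corrected HR lies inside the tabulated range of 1.75 to 1.85.** That range reflects uncertain prevalence. At each given prevalence the HR still rises.

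A stronger reading is tempting: that accrual was slow, so events and power will be far lower. The documents give no activation date for the study or for Amendment 7, and no observed accrual rate. Suppose that the first 260 patients took 3.0 to 4.5 years and later accrual runs at 8 to 16 per month. If the analysis falls at 196 IDFS events (Section 9.2.2), there are about 70 to 81 post-landmark events and power is 66 to 72%. If it falls 3 years after accrual ends (Section 9.5), there are 87 to 109. Slow accrual can therefore lower or raise the count, and a downward-only range is not supported.

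**Conclusion.** The point holds at modest size. On the plan's own accrual, follow-up and hazards, with 400 evaluable patients from the last 515, about 84 to 86 RFS events count in the landmark analysis. Power at HR 1.75 is about 74-75%, and the HR detectable with 80% power is about 1.82. The plan's calculation from 100 events is sound; what fails is the transfer of those 100 events to a later-enrolled, landmark-restricted cohort.

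The result rests on exponential times, uniform accrual, about 260 patients enrolled before CTC blood began, and exactly 400 evaluable patients. If Amendment 7 was activated well after June 2019, fewer than 515 patients remain and the shortfall grows; if more than 400 are evaluable, it shrinks. Section 9.5.2 describes the work as exploratory, without multiplicity adjustment, and no sample size or stopping rule depends on it. Severity is low.

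**What to change.** In Section 9.5.2, replace the carried-over 100 with the expected post-landmark RFS events among patients enrolled after Amendment 7, and restate the minimum HRs. With 400 evaluable patients and about 85 events these are about 1.82 at 35% positivity, and roughly 1.90, 1.85, 1.83 and 1.84 at 20%, 25%, 30% and 45%.

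State the assumptions beside them: the number of evaluable pairs, noting that about 466 would restore 100 post-landmark events, and whether the analysis is timed by 196 IDFS events or by 3 years after accrual. Show any slower-accrual scenario only as a sensitivity analysis under both timings. Limit the representativeness statement in Section 1.7 to the tissue cohort.

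The cost is a wording change and a slightly less favourable stated figure. No patients or procedures are added.

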9.5.3 To-be-defined Exploratory Correlative Objectives

The association of detection of plasma tumor cell-free DNA tumor-specific mutations prior and after study therapy, its change over time and long-term outcome (RFS) will be explored. An amendment or proposal for this and any additional correlative science studies to be performed on biological samples will be submitted to CTEP, NCI for review and approval according to NCTN guidelines. Amendments to the protocol and/or proposals for use of biological samples will include the appropriate background, experimental plans with assay details, and a detailed statistical section. Samples for testing will not be released for testing until the appropriate NCI approvals have been obtained.

9.6 PRO Study

The study will assess the difference in health-related quality of life (HRQL) between two chemotherapy arms and to describe the rate of neurotoxicity over time in the platinum arm, the rate of medication adherence in the capecitabine arm and the rates of amenorrhea in both arms.

All participants enrolled on the main study are potentially eligible for the PRO assessments after its activation in addendum #4. Patients (regardless of molecular subtype) will be enrolled consecutively for the PRO study until reaching the target sample size for the PRO primary endpoint (i.e., 362 patients with baseline PROs assessments, see Section [9.5.1](#)). PROs assessment for HRQL, neurotoxicity or ovarian function will not be administered in the rest of the patients enrolled for the assessment of the clinical outcomes. The adherence measure (Medication Adherence Scale) for capecitabine will be descriptive and administered to all patients in this cohort.

Rev. Add#5

9.6.1 Statistical Consideration for PRO Endpoints

The primary objective of the PRO study is to compare HRQL between the chemotherapy arms. HRQL measures will be assessed at baseline, and at day 1 of cycle 3 (at 6 weeks), and 6 and 15 months after the start of study chemotherapy (dated at Day 1 of Cycle 1).

These time-points have been chosen as they will allow us to capture the acute difference in side-effects following receipt of chemotherapy, while following long enough to ensure that acute differences in side effects have resolved. Differences in symptom burden and HRQL at 15 months would be considered persistent and unlikely to improve significantly with further follow up. The study hypothesis is that HRQL between the two arms will differ significantly at all time points after baseline (i.e. the platinum chemotherapy group will report higher HRQL at all time-points). The null hypothesis is that patients on the two arms have same overall HRQL at these time points.

The primary endpoints for the PRO objective are HRQL at 6 months and 15 months after the start of study chemotherapy. The type I error rate is split between the two primary endpoints to control the overall one-sided type I error rate at 2.5% for the PROs analysis. Specifically, the one-sided type I error rate is 1.0% for HRQL test at 6 months after the start of chemotherapy and 1.5% for HRQL test at 15 months after the start of chemotherapy.

HRQL will be measured by the FBSI Treatment Side Effects (TSE) subscale score in the study, an aggregate score of 4 items from the NCCN-FACT FBSI-16 scale. Higher score represents better HRQL (score range 0-16). Based on Garcia's study (Value in Health 2012), the minimally important difference (MID) for the FBSI-TSE is 1.5 points, and the standard deviation (SD) for the score is about 3.7. A total of 326 patients will be needed to provide a 90% power to detect an effect size (i.e., MID/SD) of 0.4 at 6-months post baseline, using two-sample t test with one-sided type I error rate of 0.01. For HRQL comparison at 15 months, 290 patients would be needed for this test with one-sided type I error rate of 0.015 and 90% power. Assuming an overall attrition rate of approximately 12% by 6 months after the start of chemotherapy and 20% by 15 months after the start of chemotherapy for the PROs assessment in both arms, it is expected that about 362 patients will be needed for the primary analysis for HRQL in the study to provide the 326 patients for the HRQL test at 6 months after the start of chemotherapy and the 290 patients for HRQL test at 15 months after the start of chemotherapy.

Rev. 9/17
Rev. Add#5

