9.6.2 Analysis Plan for PRO Endpoints

PROs endpoints will be analyzed at the final analysis time for the primary endpoint. Any participants who take the PROs surveys at more than 1 time-point will be eligible for analysis. The primary endpoint for HRQL is FBSI TSE subscale score at 6 and 15 months after the start of chemotherapy. The primary endpoint of ovarian function is rate of amenorrhea at 15 months. Amenorrhea is defined as the absence of menses without secondary reason (e.g., pregnancy, oophorectomy or receipt of LHRH agonist, etc.) for the whole 6 months prior to the 15-month survey (i.e., no menses between 9 and 15 months). The primary analysis of HRQL will be assessed in all eligible patients. The primary analysis of rate of amenorrhea will be assessed in women aged 18-49 at enrollment who are premenopausal at cancer diagnosis.

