In all analyses, P-values will be two-sided. A level of 2.0% will be considered statistically significant for HRQL comparison at 6 months after the start of chemotherapy between two arms. A level of 3.0% will be considered statistically significant for HRQL comparison at 15 months after the start of chemotherapy between two arms. For all other analysis, a level of 5% will be considered statistically significant. No adjustment will be made for multiple comparisons for secondary and exploratory endpoints.

For neurotoxicity (platinum arm) and adherence (capecitabine arm), it will be descriptive only. Neurotoxicity is measured by the FACT-GOG/NTx 11-item subscale score at each time point. The FACT-GOG/NTx subscale score is calculated in a similar way as that for HRQL endpoint. Mixed effect model will be constructed as an exploratory analysis to estimate the time profile of neurotoxicity in the platinum arm. For adherence for capecitabine, the distribution of the

adherence score will be displayed via box-and-whisker plot. The proportion of high, medium and low adherence will be calculated along with the binomial exact 95% confidence interval. The adherence score for each cycle will be calculated. The reasons for non-adherence will be summarized.

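### The fixed split of the PRO alpha between 6 and 15 months is valid, but weighted Holm with the same starting levels would be more powerful at no cost in type I error

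*Combined protocol and SAP*

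**What the plan says.** Section 9.6.1 makes HRQL (the FBSI treatment side effects subscale) at 6 and at 15 months the two primary PRO endpoints and divides the alpha between them: "The type I error rate is split between the two primary endpoints to control the overall one-sided type I error rate at 2.5" percent. The 6-month share is explicit: "the one-sided type I error rate is 1.0% for HRQL test at 6 months after the start of chemotherapy". The remaining 1.5%, also one-sided, goes to 15 months.

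Section 9.6.2 turns these shares into two-sided decision levels. For 6 months it reads: "A level of 2.0% will be considered statistically significant for HRQL comparison at 6 months after the start of chemotherapy between two arms". The matching sentence for 15 months sets 3.0%. Neither level depends on the result of the other test. All remaining PRO analyses use 5% without multiplicity adjustment.

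Both tests fall at one analysis: "PROs endpoints will be analyzed at the final analysis time for the primary endpoint". Section 9.6.1 also gives the hypothesis behind the comparison: "The study hypothesis is that HRQL between the two arms will differ significantly at all time points after baseline".

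**The concern.** A split in which each test keeps its own level whatever happens to the other is weighted Bonferroni. Weighted Holm starts from the same levels but, once one hypothesis is rejected, tests the other at the full one-sided 2.5%. It rejects everything the fixed split rejects and sometimes more, under the same strong familywise bound. Because the two tests are done together, nothing in the design stands in the way.

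At stake are results in a narrow band. If 6 months is won, a 15-month one-sided p between 0.015 and 0.025 is declared non-significant. If 15 months is won, the same happens to a 6-month p between 0.010 and 0.025. In both cases an equally rigorous rule would reject. For example, after a clear 6-month win a two-sided p of 0.04 at 15 months fails, while the same p on a secondary PRO comparison counts as significant.

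**Working it through.** **Inputs.** From Section 9.6.1: one-sided levels 0.010 and 0.015, effect size 0.4 (MID 1.5, SD about 3.7), 90% power, 326 patients at 6 months, 290 at 15 months, 362 enrolled, attrition 12% and 20%. From Section 9.2: 1:1 allocation. The correlation between the 6- and 15-month scores is not in the documents. It is assumed, over the range 0 to 0.7.

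**The plan's own figures.**
- Alpha: 0.010 + 0.015 = 0.025, as stated.
- N = 4(z_α + z_β)²/d². At 6 months, 4(2.326 + 1.282)²/0.4² = 325.4, so 326 as stated.
- At 15 months, 4(2.170 + 1.282)²/d² = 298 with d = 0.40, and 290 with d = 1.5/3.7 = 0.405. The stated 290 is thus reproduced at the unrounded ratio.

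**Power of each test.** The mean of the test statistic is d√N/2, which is 0.4√326/2 = 3.611 at 6 months and 0.4√290/2 = 3.406 at 15 months.
- 6 months: Φ(3.611 − 2.326) = 90.06% at 0.010; Φ(3.611 − 1.960) = 95.06% at 0.025.
- 15 months: Φ(3.406 − 2.170) = 89.17% at 0.015; Φ(3.406 − 1.960) = 92.59% at 0.025.

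**Both time points, correlation 0, by hand.**
- Fixed split: 0.9006 × 0.8917 = 80.3%.
- Weighted Holm needs both p-values ≤ 0.025 and at least one at its starting level: 0.9506 × 0.9259 − (0.9506 − 0.9006)(0.9259 − 0.8917) = 0.8802 − 0.0017 = 87.8%.
- 6 months alone under Holm: 0.9006 + 0.0500 × 0.8917 = 94.5%. 15 months alone: 0.8917 + 0.0342 × 0.9006 = 92.3%.

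**Other correlations.** These come from the bivariate normal distribution, with the score correlation multiplied by √(290/326) to give the correlation of the test statistics.

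| Score correlation | Both, fixed | Both, Holm | 6 mo, Holm | 15 mo, Holm | At least one, either rule |
|---|---|---|---|---|---|
| 0 | 80.3% | 87.8% | 94.5% | 92.3% | 98.9% |
| 0.3 | 81.4% | 88.3% | 94.1% | 92.0% | 97.8% |
| 0.5 | 82.5% | 88.8% | 93.7% | 91.8% | 96.8% |
| 0.7 | 83.8% | 89.4% | 93.3% | 91.6% | 95.4% |

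The last column is the same for both rules because the first rejection always has to be made at a starting level.

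**Familywise error.** If both nulls are true, any rejection needs p ≤ 0.010 at 6 months or p ≤ 0.015 at 15 months, so the error is at most 0.025. If one null is true, its false rejection needs p ≤ 0.025. The bound holds at any correlation. Simulation gave 2.2% to 2.5%.

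**Sensitivity to attrition.** The stated attrition leaves 362 × 0.88 = 318.6 and 362 × 0.80 = 289.6 patients. Power for both is then 79.5-83.3% under the fixed split and 87.4-89.1% under Holm, so the gain is much the same.

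**The case against.** The strongest reply is that nothing is wrong with the plan. The split controls the error rate it sets out to control. Each test was sized at its own reduced level, so the price was paid in sample size. The chance of showing at least one primary time point is already 95-99%. HRQL is a secondary objective (2.2.5), and IDFS, OS and toxicity are untouched. All of this stands, and it limits the point to efficiency.

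Two further limits also stand.
- The gain of 6 to 7 points is in joint power, for which the plan sets no target. For 15 months alone the gain is 2 to 3 points.
- A reader might infer that the split costs power for the hypothesis of a difference at every post-baseline time point. That hypothesis includes day 1 of cycle 3, which is not a primary endpoint and has no share of the 2.5%, so recycling between 6 and 15 months does not power it. If both time points really had to be significant, no split would be needed and each could be tested at 2.5%. Holm fits the plan as written, where either time point may be claimed on its own.

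A reader might also infer that the 15-month HRQL result is the one most needed for counselling. Section 1.8 asks for short- and long-term HRQL effects alike. What it singles out for counselling is long-term neurotoxicity, which Section 9.6.2 analyses only descriptively. Larger gains can be shown at an effect size of 0.3, but that is 0.3 × 3.7 = 1.1 points, below the plan's own minimally important difference of 1.5.

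Fixed levels do give simpler simultaneous confidence intervals. The plan promises none for the PRO endpoints, so little is lost.

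**Conclusion.** The fixed split is valid and gives about 90% power at each time point, but it is dominated by weighted Holm with the same weights. That Holm rejects at least as often within the same bound depends on no assumption about correlation. The size of the gain does depend on one. For correlations of 0 to 0.7, with 326 and 290 patients and effect size 0.4, power for both rises from about 80-84% to 88-89%, at 6 months from 90% to 93-95%, and at 15 months from 89% to about 92%.

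It would be tempting to call the second test too strict, or the PRO study underpowered. The documents support neither reading: type I error is controlled as stated, and there is no shortfall against any stated power. The power to show at least one time point does not change, and cycle 3 stays outside the alpha plan. The point is a free improvement.

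**What to change.** Keep the starting levels and add one sentence to each section.
- **9.6.1:** *The two primary HRQL hypotheses are tested by the weighted Holm procedure with starting one-sided levels of 1.0% (6 months) and 1.5% (15 months); if either is rejected, the other is tested at one-sided 2.5%.*
- **9.6.2:** *If the 6-month comparison is significant at two-sided 2.0%, or the 15-month comparison at two-sided 3.0%, the other is tested at two-sided 5.0%.*

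The change must be specified before any PRO comparison by arm is examined. The trial is open-label (Section 9.1) and PRO collection began with addendum #4 (Section 9.6), so the amendment should record that no such comparison had been seen. The documents do not show whether the PRO analysis has already taken place. If it has, the fixed levels should stand.

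The cost is two sentences. Sample size, data collection, starting levels and the overall one-sided 2.5% are unchanged.
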